Study Procedures: A) Subjects: The target study population is older adults with mild cognitive impairment who have insomnia. B) Recruitment and Screening: We will recruit 27 eligible participants from three sources: 1) Division of Geriatric Medicine Division Ralston House clinic (on hold due to Covid), 2) PennSeek, and 3) Recruitment Database. After consent, subjects will be screened for key inclusion criteria. First, they must answer yes to one of the insomnia screening questions and score within the a 28-36 range on the TICS. Participants will be asked if it takes them longer than 30 minutes to fall asleep on most nights and/or if they are awake for more than 60 minutes during the nighttime period. Next, they will receive (either by mail or contactless delivery to their door) actigraph device and a tablet to complete a sleep diary for a period of one week. Once insomnia inclusion criteria are confirmed from the actigraph and diary data, we will contact participants by phone to schedule Visit 1 via videoconference. C) Randomization: All retained participants will be randomly allocated (1:1) to either intervention or control arm. D) Baseline (pre-treatment) assessments, collected at Visit 1, include sleep measures and measures of health related quality of life, physical activity, cognition, social activity, and blood samples. E) Intervention: A 4-week intervention (see intervention description below) will be provided to subjects randomized to the intervention group. Sleep diaries will be completed and actigraph device worn for all four weeks of treatment, in both groups. F) Post-intervention and Follow-up data collection (visit 2 week 5; visit 3 week 16): All baseline assessments will be repeated immediately post- intervention and at three months post-intervention follow-up (sleep measures and measures of health related quality of life, physical activity, cognition, social activity, and blood samples; one week sleep diary + actigraphy). G) Demographics: Data on demographics and other information (see measurement section) will be assessed by questionnaires at baseline, post-intervention and follow-up. Intervention: The intervention will include a meaningful activity protocol during the day and Assistive Relaxation Therapy at night. The personalized meaningful activity protocol will be developed based on the individuals factors contributing to insomnia, typical daily circadian profile, functional status, and preference for activity. The individuals typical circadian profile will be calculated from the one-week baseline accelerometer data using algorithms previously developed by [name] (co-mentor) and research team. The intervention will be broken into: 1) Sleep Hygiene Education, including content on routine, stimulus control principles, food/drink/substance intake (caffeine, alcohol, etc.), activity, naps, etc; 2) Meaningful Activity Modules a) Physical Activity, including content from the Go4Life Campaign (NIA) on endurance, strength, balance, and flexibility b) Cognitive Activity including various cognitively stimulating games and exercises such as cross-word puzzles and c) Social engagement including identifying social support persons, group activities in the area and using technology to stay connected; 3) Assistive Relaxation Therapy (ART), a breath-based relaxation application that is coupled with a physical anchoring task. After reviewing baseline assessments to determine etiological risk factors contributing to the insomnia, each participant and the PI will construct their meaningful activity plan. Thus, study participants in the intervention arm will receive (1) tablet computer with Ditti application (for ART) and REDCap application, sleep education material, and meaningful activity modules; (2) Actigraph wrist watch device. They will be instructed how to use the tablet and encouraged to use the tablet. They will be asked to complete the daily sleep diary on the tablet, use the activity modules daily as pre-determined times personalized to the participant, use ART when they get in bed and if they awake during the night to help them with their insomnia symptoms for a four-week period. They will be asked to wear the actiwatch on the non-dominant wrist to monitor sleep/wake patterns. Participants will have weekly to biweekly phone consultation with the study interventionist to receive guidance and adjustment on activity plans. Based on previous research,

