
physical, social, or cognitive activity has shown significant improvement in sleep in 2-4 weeks and ART therapy has improved sleep latency in just two weeks. Thus, we feel confident that a 4 week intervention period is sufficient and justified. As per NIH guidelines, we are providing additional details related to the intervention relevant for assessing Human Subjects Safety. The following components which will be used for the four-week intervention period. Tablet computer connected by wireless cellular phone data. Tablet-enabled sleep diary: The Sleep Diary will be administered via the REDCap, utilizing the MyCap feature. Sleep Education Information: Sleep education/sleep hygiene information will be loaded to the tablet; participants will also receive a print copy. Meaningful Activity Modules: There will be three modules related to physical, social and cognitive stimulating activity. These will be loaded to the tablet; participants will also receive a print copy. Assisted Relaxation Therapy (ART) will be loaded onto the tablet via Ditti application. We will ask the study participant to engage in an anchoring task (finger tap) on the tablet screen at the exhalation point of the breathing cycle while they are lying in bed trying to sleep. Study participants will be asked to use the ART intervention every night as they are trying to fall asleep, or when they wake up at night. They will use it every night for four weeks. For ART intervention to work, it must be used on a nightly basis when in bed. It will be administered via the tablet. These technologies do not constitute a medical device as per FDA guidance related to mobile device technologies. Actiwatch Spectrum Plus: Each participant will be given an Actiwatch Spectrum Plus (Koninklijke Philips, N.V.), a piezoelectric accelerometer worn on the non-dominant wrist. Movement data are sampled at a rate of 32 Hz, and activity counts are recorded in 60-second epochs. Additionally, the watch has Silicon photodiode light sensors, and a button that enables participants to signal when they first try to fall asleep and when they get out of bed in the morning. The button can also be used to signal naps. Periods of activity and inactivity are analyzed in order to estimate sleep/wake status. Computer programs are used to derive levels of activity/inactivity, rhythm parameters and daytime naps. Wrist actigraphy monitoring has been shown to be a reliable way to objectively monitor sleep-wake cycles. Control arm: The control arm will consist of sleep education materials. They will be asked to complete the tablet-enabled sleep diary and wear an actigraph device on the non-dominant wrist. See attached for protocol table.

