We do not believe there are any major risks associated with the proposed protocol. There is minimal risk associated with finger pricks for blood samples, physical activity, and study burden. We will explain associated risk to the participants. Other potential risks to participants are fatigue from data collection, stress in response to self-report instruments or concerns related to confidentiality. In addition, the participant may experience discomfort from sleeping with the wrist watch device, but that usually subsides after the first night. If the participant cannot tolerate the watch, he/she will be instructed that removal of the watch is allowed. Participant burden, specifically fatigue, is the most likely risk related to this study. To minimize fatigue during data collection, we chose only the most relevant self-report instruments. However, given that this is an older adult population with cognitive impairment; we will offer the participant the opportunity to take breaks. It is possible that some participants may become anxious or stressed during data collection because of the questions asked, the burden of data collection, or for other personal reasons. Stress is judged to be low likelihood because the instrument questions are not highly intrusive or sensitive. However, should this occur, the participant will be asked if they would like to terminate or delay data collection. Loss of confidentiality is considered very low likelihood given the protections we will have in place and our experience in systems of protecting private information. Intervention: The study poses minimal risks to subjects beyond standard clinical care for insomnia. Sleep hygiene is a standard clinical recommendation for insomnia, and thus does not pose any additional risks to the subject beyond standard clinical care. Furthermore, the relaxation intervention component can reduce the risk of falls or daytime sleepiness associated with the standard of care treatment, conventional CBT-I. The tablet screen background is black for the sleep diary to avoid excessive light exposure at night, and the tablet screen is set to black when using the ART intervention in bed. The tablets are locked to prevent use of other applications. Plan to address risk: Finger prick via a Lancet for blood samples might result in occasional bruising, pain, or local reaction. All blood samples will be taken by the participant using precise methods provided to them. Physical Activity: In very rare occasions, the subject may fall or get injured during physical activities. These adverse events should be minimized by using personalized physical activity plans, which will be developed/designed based on the subjects personal features by the PI to be most suitable for the subject. The activity intervention will be based on an existing NIH-funded activity protocol for older adults. Any occurrence of adverse events will be immediately reported to the IRB at the University of Pennsylvania. Wrist watch discomfort: The subject may experience discomfort from sleeping with the wrist watch device, but that usually subsides after the first night. If the subject cannot tolerate the watch, he/she will be instructed that removal of the watch is allowed. Fatigue: We estimate screening and consent to take 30 minutes, quantitative data collection 20 minutes; instructions for actigraphy and sleep diary 5-10 minutes; blood samples 5 minutes. We anticipate developing the meaningful activity plan to take 30 minutes to one hour. Stress: As the PI, I will be overseeing data collection. I am a registered nurse with a masters degree specialized in the care of older adults and a PhD. Thus, I am well trained to be supportive and helpful to the participants should they become anxious or stressed in response to survey questions. If participants do become stressed, data collection will be delayed to tend to the participants emotional needs. Data collection will resume if and when the participant is ready to proceed.

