Trial monitoring will be done by a safety monitoring committee, which includes the PI, primary mentor ([name]) a statistician ([name]) and an expert in the care of older adults ([name]). We will evaluate the progress of the study on a monthly basis, including periodic assessments of data quality (safety and integrity) and timeliness, recruitment, accrual and retention, participant risk versus benefit, and other factors that can affect study outcome; consider factors external to the study when relevant information becomes available, such as scientific or therapeutic developments that may have an impact on the safety of the participants or the ethics of the trial; review study performance; and discuss the resolution of problems. Furthermore, we will monitor adverse events (AEs), including serious adverse events (SAEs) and unanticipated problems (UPs). An Adverse Event is any untoward medical occurrence in a patient or clinical investigation participant and which does not necessarily have a causal relationship with this treatment. Participants will be queried regarding any changes in their health and medications at each contact. The informed consent document will list the daytime and after hours contact information for the site Principal Investigator. All AE and SAE reporting will be done in adherence with IRB guidelines; the PI will notify the IRB within 48 hours of any serious possible or potentially study-related AEs. The report will include the description of the AEs and any actions taken by the PI. SAEs in this population include, but are not limited to death, hospitalization, evidence of abuse, suicidal ideation, and medical emergencies. The PI will also keep a log of all AEs. Any deviations related to the protocol will be reported to the IRB using a deviation form immediately upon the discovery of the deviation. Given the non-invasive nature of the intervention, the team does not anticipate AEs beyond the average rate of these events in this population. The literature in the field will be continually appraised by the team. If any team member uncovers new information that would impact the safety of the participants or the ethics of our study, the PI and entire mentoring team will discuss the issues. At this time, given the low risk of the intervention, there is no plan for interim analyses or any stopping rules.

The following documents are currently attached to this item:

There are no documents attached for this item.

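### Harms are asked about at contacts, and the intervention arm appears to have 4 to 6 scheduled contacts after randomization against 2 for controls, so adverse-event counts by arm would not be comparable; separately, two IRB reporting statements differ

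*Combined protocol and SAP*

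**What the plan says.** **How harms are found.** Data and Safety Monitoring ties the questioning to contacts: "Participants will be queried regarding any changes in their health and medications at each contact". It gives no separate schedule for adverse-event questions.

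**Contacts in the intervention arm.** The intervention part of Procedures says: "Participants will have weekly to biweekly phone consultation with the study interventionist to receive guidance and adjustment on activity plans". The sentence comes after the list of what the intervention arm receives ("Thus, study participants in the intervention arm will receive (1) tablet computer with Ditti application (for ART) and REDCap application") and after the statement that "each participant and the PI will construct their meaningful activity plan".

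**Contacts in the control arm.** Procedures says: "The control arm will consist of sleep education materials. They will be asked to complete the tablet-enabled sleep diary and wear an actigraph device". No scheduled call is described.

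**Contacts in both arms.** Procedures schedules visits at week 5 and week 16. Administration of Surveys and/or Process adds questionnaires on medication use, naming sleep medication and benzodiazepines, and on medical conditions at baseline, post-intervention and follow-up, without restriction by arm. The Analysis Plan mentions that participants can be called to remind them about the diary; these calls are not scheduled.

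**Reporting to the IRB.** Potential Study Risks says: "Any occurrence of adverse events will be immediately reported to the IRB". Data and Safety Monitoring says: "the PI will notify the IRB within 48 hours of any serious possible or potentially study-related AEs". It adds that the investigator logs all adverse events and that reporting follows IRB guidelines.

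**The concern.** If the same question is put more often in one arm, more events will be recorded there, whatever the true rates. That matters here for three reasons. Participants have cognitive impairment, so recall of minor events over four weeks may be poor. Potential Study Risks names falls and injury during physical activity as possible harms of the intervention, so a raw count by arm would invite a causal reading. And with 27 participants, one or two extra recorded events would change how the arms look.

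Medication changes are covered by the same contact-based rule. Sleep-aid use is an entry exclusion and could affect sleep latency, so it is reasonable to ask whether new use is also recorded unequally.

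The reporting statements raise a separate issue: staff need one rule for which events go to the IRB, and when.

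**Working it through.** The plan states no figure on this point, so there is none to reproduce. The check has four parts.

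**1. Scheduled contacts after randomization.** The baseline visit is left out because both arms have it. The contact at which the activity plan is built is left out because its timing is not given.

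| | Intervention | Control |
|---|---|---|
| Calls, weekly to biweekly over 4 weeks | 4/2 = 2 to 4/1 = 4 | 0 |
| Visits, weeks 5 and 16 | 2 | 2 |
| Total | 4 to 6 | 2 |

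The ratio is 4/2 = 2 to 6/2 = 3. No calls are described for either arm after week 5, so the imbalance arises in the treatment weeks.

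**2. What equal true rates could look like.** The documents give no detection rates, so both models below rest on assumptions.

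*Recall decay.* Events occur evenly over four weeks. Each is reported at the next query with a probability that halves every h weeks. With T weeks between queries and λ = ln 2 / h, the share reported is (1 − e^(−λT)) / (λT). Controls are queried once, at 4 weeks.

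| h (weeks) | Control, T = 4 | Biweekly calls, T = 2 | Weekly calls, T = 1 | Ratio to control |
|---|---|---|---|---|
| 1 | 0.338 | 0.541 | 0.721 | 1.60 to 2.13 |
| 2 | 0.541 | 0.721 | 0.845 | 1.33 to 1.56 |
| 4 | 0.721 | 0.845 | 0.918 | 1.17 to 1.27 |

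*Constant detection.* Each query finds an earlier event with probability p, so n queries find it with probability 1 − (1 − p)^n. Both visits count in both arms, and calls fall at the ends of weeks. Controls have n = 2. With weekly calls, events in weeks 1, 2, 3 and 4 face n = 6, 5, 4 and 3. With biweekly calls they face n = 4, 4, 3 and 3.

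| p | Control | Biweekly calls | Weekly calls | Ratio to control |
|---|---|---|---|---|
| 0.2 | 0.360 | 0.539 | 0.622 | 1.50 to 1.73 |
| 0.5 | 0.750 | 0.906 | 0.941 | 1.21 to 1.26 |
| 0.9 | 0.990 | 0.999 | 1.000 | 1.01 |

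*In events.* Take 27/2 = 13.5 per arm, weekly calls, recall decay, and an assumed true rate of 10% or 30%. The expected excess in the intervention arm is 13.5 × rate × (difference in share reported). The smallest value is 13.5 × 0.10 × (0.918 − 0.721) = 0.27 events (h = 4). The largest is 13.5 × 0.30 × (0.721 − 0.338) = 1.55 events (h = 1).

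**3. Sleep medication.** The questionnaire is due at three time points in each arm, so scheduled capture is equal. The contact rule adds 2 to 4 further occasions in the intervention arm only. What may differ is the recording of short-lived use between visits, and of when it began.

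**4. The two reporting statements.**

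| | Potential Study Risks | Data and Safety Monitoring |
|---|---|---|
| Which events | Any adverse event | Serious, and possibly or potentially study-related |
| How fast | Immediately | Within 48 hours |
| Other events | No separate rule | Logged by the investigator; IRB guidelines apply |

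A non-serious fall would be reported at once under the first statement and is not covered by the 48-hour rule in the second.

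**The case against.** **The contact difference is partly inferred.** The call sentence speaks of participants without naming an arm, and Procedures refers to a protocol table that is not available here. This is a fair caveat. Still, the calls are for adjusting activity plans, and only the intervention arm has these. Reminder calls are possible in either arm but depend on missed diary entries, so they do not equalize the questioning.

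**No arm comparison of harms is planned.** This stands. The Analysis Plan contains no between-arm adverse-event analysis, and there are no interim analyses or stopping rules. The safety committee considers risk against benefit monthly, and a reader might infer that it compares counts by arm, but the text does not say so. The point therefore concerns any arm-wise summary that is produced, not a specified test.

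**Sleep-aid use.** A reader might infer from the contact rule that new sleep-aid use is under-recorded in controls. The questionnaire given to both arms at all three time points answers most of that.

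**Size.** Setting 3 to 5 queries against 1 at p = 0.5 gives 0.875/0.5 = 1.75 to 0.969/0.5 = 1.94. That leaves out the week 16 visit and treats every event as if it preceded every call. Correcting both brings the ratio down to about 1.2 to 1.26 at the same p.

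**Reporting.** A reader might infer that following either statement breaches the other. That is so in one direction only: immediate reporting of every event also meets the 48-hour rule. The sentence in Potential Study Risks follows text on physical-activity injuries and may be meant only for those, though its wording has no such limit.

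**Conclusion.** The point holds as a minor one. On the best reading of Procedures, harms questioning is unequal by design: 2 to 4 scheduled calls against none during treatment, and 4 to 6 scheduled contacts against 2 overall. Arm-wise adverse-event counts that pool all contacts would not be comparable. The likely direction is an apparent excess in the intervention arm. An excess of about 1.2 to 2 times is an illustration, not an estimate; it falls to about 1.01 if each question finds 90% of events. At this sample size it amounts to roughly 0.3 to 1.6 events under the assumptions shown for weekly calls.

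For sleep medication, only brief use between visits and its timing are open to unequal recording.

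The two IRB statements differ in scope and timing. Staff who follow Data and Safety Monitoring alone could fall short of Potential Study Risks. This review does not say which is right.

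**What to change.** 1. State in the Analysis Plan that any between-arm harms summary uses the questioning at the common visits (weeks 5 and 16). List events first learned at intervention calls separately, and record for each event the contact at which it was first learned. This costs a few sentences and one field in the event log.
2. For participants still in treatment, a weekly health-and-medication item could be added to the tablet diary that both arms complete. It adds a small burden and one form item. Its value is limited: Current Status of Study shows enrolment closed with 27 enrolled, and the item cannot recover treatment weeks already completed. It could not support a full-sample comparison.
3. Reconcile Potential Study Risks and Data and Safety Monitoring into one statement of which events are reported to the IRB, how fast, and which are only logged. If the sentence in Potential Study Risks is meant for physical-activity injuries alone, say so. This is a wording change.
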